12.6 Protocol Amendment 2 Summary

Title: A PHASE 3, MULTICENTER, OPEN-LABEL 52-WEEK EXTENSION STUDY TO EVALUATE THE LONG-TERM SAFETY AND TOLERABILITY OF ORAL ATOGEPANT FOR THE PREVENTION OF MIGRAINE IN JAPANESE PARTICIPANTS WITH CHRONIC OR EPISODIC MIGRAINE

Protocol 3101-306-002

Date of Amendment 2: 22 December 2021

Amendment Summary

This amendment includes changes made to Protocol 3101-306-002 Amendment 1, dated 25 November 2019. This protocol was amended to add De Novo EM Participants and to correct minor editorial errors.

The table below provides details on the content changes that were made in the protocol, and a brief rationale with these changes. Minor editorial and document formatting revisions have not been summarized.

Section	Revision	Rationale
Title Page	Left cell: Allergan (AbbVie Company) Signatory: Right cell: [REDACTED] [REDACTED], Clinical Neuroscience Development	Allergan was acquired by AbbVie.
Protocol Summary	Updated.	To reflect changes in the body of the protocol.
Table 1 Schedule of Visits and Procedures	Updated.	To reflect changes in the body of the protocol.
Table 2 Schedule of Procedures for Remote Visits (Amendment 2 table)	New table was added.	To outline remote visit procedures in the event of a COVID-19 infection.
1.2 Overview of Atogepant	Recent study results and approval of atogepant for the preventive treatment of EM in adults were added.	To reflect the current status of the atogepant program.

Section	Revision	Rationale
3.1 Structure	Updated.	To reflect addition of De Novo EM Participants, which created 2 cohorts (De Novo EM Participants and 3101-303-002 Completers), a 4-week screening/baseline period for De Novo EM Participants only, and a larger sample size (changed from 140 participants to 170 participants [30 De Novo EM Participants enrolled at selected sites only]). All references to lead-in Study 3101-305-002 were removed from the protocol.
3.2 Data Safety Monitoring Board	Updated.	To reflect the involvement of a DSMB.
4.1 Number of Participants	Updated.	To reflect addition of De Novo EM Participants.
4.2 Study Population Characteristics	Updated.	To reflect the 2 cohorts.
4.3.1 Inclusion Criteria	Updated.	To reflect inclusion criteria applicable for all participants.
4.3.2 3101-303-002 Completers (Amendment 2 section)	New section was added.	To reflect inclusion criteria for 3101-303-002 Completers only.

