### Summary of Changes from the Final SAP to SAP Amendment 1:

Date	Section: Description	Reason
03/18/21	Added EQ-5D-5L text in Sections 5.3.4.5 and 6.4.3	Consistent with 3101-301-002 and -302 HO SAP text
03/18/21	Section 5.1: replaced 'extension' to 'lead-in' in baseline definition.	to align with other extension Atogepant studies
03/18/21	Section 6.3.1: replaced 'White' by 'Asian'	study is Japanese
03/18/21	Section 6.3.2: removed 'migraine severity'	specified neither in the study protocol, nor in prior Atogepant studies.
03/18/21	Table 6-1: removed 'Insulin'	Because it is not collected.
03/24/21	Added 'evaluable baseline' to Section 4.	
5/20/21	Updated analysis visit windows	
5/20/21	Added 95% CI for primary and key secondary endpoints from 3101-303-002 study	Consistent with current Atogepant LTS extension studies (except for study 311 due to small sample size).
7/6/2021	In Section 1.1, added six endpoints, Change from baseline in monthly severe headache days at each monthly period, Change from baseline in monthly cumulative headache hours at each monthly period, At least a 5-point improvement (decrease) from baseline in total HIT-6 score at each monthly period, Change from baseline in the EQ-5D-5L VAS score at each monthly period, Change from baseline in MIDAS absenteeism score (Questions 1, 3, and 5) at Weeks 12, 24, 36, 48, and 52, and Change from baseline in MIDAS presenteeism score (Questions 2 and 4) at Weeks 12, 24, 36, 48, and 52	To align with the protocol.
7/6/2021	In Section 5.3.1, updated analysis methods	Consistent with current Atogepant LTS extension studies (except for study 311 due to small sample size).
7/6/2021	In Section 6.3.4, updated the derivation for AIM-D total score, MIDAS absenteeism score, and MIDAS presenteeism score.	New endpoints added.
12/7/2022	In Section 1, updated the wording in introduction	To align with the protocol.

Date	Section: Description	Reason
12/7/2022	In Section 1.1, added three endpoints, Change from baseline in monthly AIM-D total score at each monthly period, Change from baseline in monthly activity level at each monthly period and Change from baseline in monthly activity limitation at each monthly period	To align with the protocol.
12/7/2022	In Section 1.2, updated study design, study schema, and schedule of activities	To reflect addition of De Novo EM Participants in Protocol Amendment 3.
12/7/2022	In Section 3, updated sample size	To reflect addition of De Novo EM Participants in Protocol Amendment 3.

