### 3. Sample Size Determination

The study sample size was driven by regulatory safety requirements for the duration and number of participants exposed rather than statistical considerations. At least 170 participants will be enrolled into this long-term, open label, safety extension study including at least 140 participants from the lead-in study (Study 3101-303-002) and approximately 30 De Novo EM Participants (from selected sites only) to meet a target of a minimum of 100 participants exposed to atogepant at 1 year.

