## 5. Statistical Analyses

### 5.1. General Considerations

- Efficacy endpoints will be analyzed descriptively based on the mITT population.
- Safety endpoints will be performed using the Safety population.
- Continuous variables will be summarized by number of participants with observed values (n), mean, standard deviation (SD), median, 1st and 3rd quartiles (Q1, Q3), minimum (min), and maximum (max).
- Categorical variables will be summarized by number of participants with observed values, events (n), frequency count (n1), and percentage of participants with observed values.
- Partial dates will be treated as missing in computation or in variable derivation unless specified otherwise, but will be listed in the data listings as they appear on the eCRF.
- For monthly endpoints, baseline is defined as assessments during the last 28 days of baseline period in the lead-in study for 3101-303-002 rollover participants, and the last 28 days of the screening/baseline period for De Novo EM Participants. For efficacy endpoints that are assessed at clinical visits, baseline is defined as the last non-missing efficacy assessment before the first dose of study intervention in the lead-in study (3101-303-002) for 3101-303-002 Completers, and the last non-missing efficacy assessment before the first dose of study for De Novo EM Participants. For each of the clinical, laboratory, vital sign, and ECG parameters, the baseline is defined as the baseline value in the lead-in study (3101-303-002) for 3101-303-002 Completers, and the last nonmissing safety assessment before the first dose of study drug for De Novo EM Participants.
- The change from baseline values will be computed as the post-baseline value minus the baseline value.
- Study intervention is treatment administered (atogepant 60 mg QD).
- All statistical analysis will be performed using SAS version 9.4 or higher.
- Medical Dictionary for Regulatory Activities (MedDRA), Version 27.0 or higher, will be used to code adverse events and medical history.
- WHO Drug Global B3 (v.202403 or higher) will be used to code medications.

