each monthly period) and for the key secondary endpoints of the lead-in 3101-303-002 study (Change from baseline in monthly headache days at each monthly period, Change from baseline in monthly acute medication use days at each monthly period,  $\geq 50\%$  improvement (decrease) in monthly migraine days at each monthly period, change from baseline in MSQ v2.1 Role Function Restrictive Domain at each monthly period, change from baseline in monthly Performance of Daily Activities domain score of the AIM-D at each monthly period, change from baseline in the Physical Impairment domain score of the AIM-D at each monthly period, change from baseline in the HIT-6 total score at each monthly period), point estimates and 95% CIs will be provided. The 95% CI for the continuous endpoints will be based on a mixed-effects model for repeated measures (MMRM). The model will include visit (derived as month) as a categorical fixed effect, and the baseline score, baseline-by-visit interaction as covariates. Restricted maximum likelihood method will be used. An unstructured covariance matrix will be used to model the covariance of within-participant repeated measurements. If the model does not converge, then simplified covariance structures will be used to fit the model in the following order: (1) Toeplitz and (2) compound symmetry. The Kenward Roger approximation ([Kenward 1997](#)) will be used to estimate the denominator degrees of freedom. Each treatment effect will be estimated by the least square mean along with the corresponding standard error and 95% confidence interval. The analysis will be performed based on all post-baseline values using only the observed cases without imputation of missing values. The 95% CI for percent improvement (decrease) in monthly migraine days at each monthly period will be based on the normal approximation to the binomial.

On a daily basis during the open-label treatment period, participants are to record into an eDiary information on the daily total duration of headache, headache specific characteristics and symptoms, the worst pain severity, and use of any acute headache pain medication. Participants will be able to report headache data, including absence of headache, for the day of the eDiary report and for the day immediately prior to the day of the eDiary report.

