### **5.3.2. Main Analytical Approach**

Descriptive statistics will be provided by visit for all efficacy endpoints based on the mITT population using the observed case (OC) approach. No inferential statistical analyses will be performed for the efficacy endpoints except where noted above.

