## 5.5. Other Analyses

### 5.5.1. Subgroup Analyses

#### Efficacy Subgroup Analyses

For all efficacy and health outcome endpoints, subgroup analyses will be performed by 3101-303-002 Completers or De Novo EM Participants and overall.

For the following efficacy endpoints, separate figures will be presented by 3101-303-002 Completers or De Novo EM Participants. The figures for over time change during the 12-Week Double-Blind treatment period and the 52-Week Open-label treatment period for 3101-303-002 CM Completers in mITT population will also be presented, for the following efficacy endpoints.

- Change from baseline in monthly migraine days at each monthly period
- Change from baseline in monthly headache days at each monthly period
- Change from baseline in monthly acute medication use days at each monthly period

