The monthly migraine days is defined the total number of recorded migraine days in the eDiary divided by the total number of days with eDiary records during each monthly period and multiplied by 28. **For baseline, a minimum of 20 days' eDiary data during the 4-week baseline period is required for the migraine days to be evaluable.** For each postbaseline 4-week treatment period, a minimum of 14 days' eDiary data during that period is required for the migraine days to be evaluable. If a participant does not have at least 14 days of diary data for a monthly treatment period, the migraine days for that period will be considered as missing. Migraine days will be derived for each participant at baseline and for each postbaseline monthly treatment period (Weeks 1-4, 5-8, 9-12, 13-16, 17-20, 21-24, 25-28, 29-32, 33-36, 37-40, 41-44, 45-48, 49-52). The same method to derive monthly migraine days will be used to derive monthly headache days, monthly acute medication use days, monthly triptan use days, monthly cumulative headache hours, monthly moderate/severe headache days, and monthly severe headache days.

If a participant confirmed that acute medications were taken and entered medications in the eDiary, then the acute medication use day will be set to 'Yes.' If a participant reports 'Yes' to the intake of allowed medication(s) to treat an acute migraine but does not list any of them in the diary, then the acute medication use days will not be counted in this situation and vice versa.

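### The 95% CI for the ≥50% responder rate uses the normal approximation, which averages below 95% coverage in a De Novo EM cohort of about 30; a Wilson interval corrects this at almost no cost

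*SAP*

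**What the plan says.** SAP 5.3.1 adds point estimates and 95% CIs for the lead-in study's primary and key secondary endpoints, one of which is ≥50% improvement in monthly migraine days at each month. Continuous endpoints get their interval from an MMRM. For the responder endpoint, the interval for improvement "in monthly migraine days at each monthly period will be based on the normal approximation to the binomial". No small-sample alternative is named.

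Under SAP 5.5.1, for all efficacy and health outcome endpoints, "subgroup analyses will be performed by 3101-303-002 Completers or De Novo EM Participants and overall". SAP 3 plans "approximately 30 De Novo EM Participants (from selected sites only"), at least 140 lead-in completers and at least 170 in total; SAP 1.2 gives 30 as a minimum for De Novo EM.

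The monthly denominator can be smaller than the cohort. SAP 6.4.2.1 requires 14 diary days in a 28-day period; otherwise "the migraine days for that period will be considered as missing". SAP 5.3.2 gives descriptive statistics "for all efficacy endpoints based on the mITT population using the observed case (OC) approach".

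SAP 2 specifies no statistical hypothesis.

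**The concern.** The Wald interval puts the observed proportion into its own standard error. With about 30 binary observations its true coverage swings with the underlying rate and usually lies below the stated level. It can also give limits above 100%, and it collapses to a point when everyone responds.

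It is the only interval the SAP gives for the ≥50% response rate, and it would be shown at 13 monthly periods. A reader of the De Novo EM columns would take it for a 95% interval when on average it is not.

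The SAP change log suggests that the method was not chosen with this cohort in mind. The CIs were added on 5/20/21 and the 5.3.1 methods updated on 7/6/2021, both with the reason "Consistent with current Atogepant LTS extension studies (except for study 311 due to small sample size"). The De Novo cohort arrived later, with protocol Amendment 2 of 22 December 2021: "This protocol was amended to add De Novo EM Participants and to correct minor editorial errors".

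**Working it through.** **Inputs.** Confidence level 95%, z = 1.96 (SAP 5.3.1). Cohort sizes 30, 140 and 170 (SAP 3). The documents give no expected response rate, so the true rate p is an assumption, shown over three ranges. Monthly denominators of 25 and 20 are also assumptions, standing for dropout or months with too few diary days.

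**Formulas**, with x responders and p̂ = x/n:

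- Wald: p̂ ± 1.96·√(p̂(1−p̂)/n)
- Wilson: [x + z²/2 ± z·√(n·p̂(1−p̂) + z²/4)] / (n + z²), with z² = 3.8415
- Exact coverage at p: the sum of Binomial(n, p) probabilities over all x whose interval contains p. This is averaged, and its minimum taken, on a grid of p in steps of 0.001.

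**Intervals at n=30.** For 27 responders:

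- Wald: 0.9 ± 1.96·√(0.09/30) = 0.9 ± 0.107, or 79.3% to 100.7%.
- Wilson: (27 + 1.921)/33.84 ± 1.96·√(2.7 + 0.960)/33.84 = 0.855 ± 0.111, or 74.4% to 96.5%.

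| Responders of 30 | Wald | Wilson |
|---|---|---|
| 15 | 32.1–67.9% | 33.2–66.8% |
| 21 | 53.6–86.4% | 52.1–83.3% |
| 24 | 65.7–94.3% | 62.7–90.5% |
| 27 | 79.3–100.7% | 74.4–96.5% |
| 30 | 100–100% | 88.6–100% |

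**Coverage at one rate.** At n=30 and p=0.9 the Wald interval contains 0.9 only for x = 23 to 28. It misses at x = 29 (90.2–103.1%; probability 14.1%), at x = 30 (4.2%) and at x ≤ 22 (0.8%). Coverage is 100 − 14.1 − 4.2 − 0.8 = 80.9%.

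**Mean coverage (minimum) over the assumed ranges:**

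| Interval, n | p 0.4–0.7 | p 0.4–0.8 | p 0.4–0.9 |
|---|---|---|---|
| Wald, 20 | 92.5% (88.4) | 92.3% (86.8) | 91.7% (80.7) |
| Wald, 25 | 93.0% (89.7) | 92.8% (88.4) | 92.2% (80.2) |
| Wald, 30 | 93.4% (90.6) | 93.2% (88.4) | 92.5% (80.9) |
| Wilson, 30 | 95.1% (92.9) | 95.1% (92.7) | 95.2% (92.2) |
| Clopper-Pearson, 30 | 96.8% (95.4) | 96.8% (95.4) | 97.0% (95.4) |
| Wald, 140 | 94.7% (93.6) | 94.6% (93.3) | 94.5% (92.0) |
| Wald, 170 | 94.7% (93.8) | 94.7% (93.4) | 94.6% (92.3) |

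**Single rates at n=30, Wald against Wilson:** 0.5, 95.7% and 95.7%; 0.6, 93.5% and 96.2%; 0.7, 95.3% and 93.0%; 0.8, 94.6% and 96.4%; 0.9, 80.9% and 97.4%.

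**Limits above 100%.** At n=30 this happens with 27, 28 or 29 responders. Its probability in one month is 0.9%, 12% and 60.5% at true rates of 0.7, 0.8 and 0.9.

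**Width.** At n=30, averaged over p from 0.3 to 0.8, Wilson is slightly narrower: 31.7 percentage points against 33.4. At p = 0.9 it is wider (21.5 against 20.1), because the Wald interval is too short there.

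**The case against.** - **The SAP does not say Wald.** A continuity-corrected normal approximation (adding 1/(2n) to each half-width) would average 95.5%, 95.4% and 95.0% at n=30 over the three ranges, and the average shortfall would disappear. That is correct, but the plain form is the ordinary reading. The corrected form still falls to 86.9% within 0.4–0.9 and still exceeds 100%. The text should name the interval in either case.
- **Cohort-level intervals are inferred.** SAP 5.5.1 calls for subgroup analyses of all efficacy endpoints but does not mention CIs. This stands as an ambiguity. If no cohort intervals are meant, only the larger groups are affected, and there the loss is negligible.
- **Wilson is not better at every rate.** At 0.5 the two are equal and at 0.7 Wald covers better. The gain is in the average and the worst case. The most striking Wald failures need a true rate near 0.9 or a month in which everyone responds.
- **The cohort may exceed 30.** At an assumed n=40 the Wald means are still only 93.8%, 93.7% and 93.3% over the three ranges.
- **The SAP was revised later with this cohort in view.** SAP 5.5.1 was added on 12/7/2022 and the efficacy subgroups were updated on 12/26/2023, so the dates alone do not prove an oversight. The log records no change of interval method, however. The study 311 exception shows only that small samples were considered elsewhere; it gives no size.
- **Nothing is decided on this interval.** Efficacy is descriptive and unranked, and SAP 5.1 says "Categorical variables will be summarized by number of participants with observed values", along with counts and percentages. A reader can rebuild any interval. This stands, and it keeps the point minor.

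**Conclusion.** The concern holds, as a minor point. Under the ordinary Wald reading, and if the intervals are shown by cohort, the De Novo EM interval at n=30 covers about 1.6 to 2.5 percentage points less than 95% on average (95 − 93.4 and 95 − 92.5). Much larger shortfalls occur near a true rate of 0.9. The shortfall grows to about 2.5 to 3.3 points if only 20 are observed in a month (95 − 92.5 and 95 − 91.7). In the completers and overall it is at most 0.5 points on average. The sizes depend on the assumed response rates and monthly denominators. The direction does not: Wald at n=20, 25 and 30 averages below 95% over all three ranges, and Wilson at n=30 averages about 95% over each.

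**What to change.** In SAP 5.3.1, replace the normal approximation with the Wilson score interval for the ≥50% responder proportion, at each month, overall and by cohort. In SAP 5.5.1, state that the 5.3.1 intervals are also given by cohort. If guaranteed coverage is preferred, Clopper-Pearson is an alternative, but it is conservative (mean 97.0% at n=30 over 0.4–0.9).

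The cost is one phrase in 5.3.1, one clarifying sentence in 5.5.1 and one program option, with no new data. Wilson limits are not symmetric about the observed percentage, and the method would differ from any normal-approximation intervals in the related extension studies.

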### **5.3.2. Main Analytical Approach**

Descriptive statistics will be provided by visit for all efficacy endpoints based on the mITT population using the observed case (OC) approach. No inferential statistical analyses will be performed for the efficacy endpoints except where noted above.

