8.8 Early Discontinuation of Participants

A premature discontinuation will occur when a participant who signed the ICF ceases participation in the study, regardless of circumstances, before completion of the study. Participants can be prematurely discontinued from the study for one of the following reasons:

- AE
- Lack of efficacy
- Lost to follow-up
- Noncompliance with study intervention (ie, atogepant)

- Pregnancy
- Protocol deviation
- Site terminated by Sponsor
- Study terminated by Sponsor
- Withdrawal by participant

Participants may voluntarily withdraw from the study at any time.

Notification of early participant discontinuation from the study and the reason for discontinuation will be made to the sponsor and will be clearly documented on the appropriate eCRF. All participants who prematurely discontinue from the study, regardless of cause, should be seen for final study assessments. The final assessments will be defined as completion of the evaluations scheduled for Visit 14/ET and Visit 15/EOS; 4 weeks after the last dose of atogepant.

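### The monthly migraine-day responder rates cover only participants with an evaluable diary month, and no supplementary rate keeps the full mITT denominator

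*SAP*

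**What the plan says.** SAP 5.3.1 lists ≥ 25%, ≥ 30%, ≥ 50%, ≥ 75% and 100% improvement in monthly migraine days as endpoints in each 4-week period. Four rules fix how they are reported.

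- **Population and approach** (SAP 5.3.2): "Descriptive statistics will be provided by visit for all efficacy endpoints based on the mITT population using the observed case (OC) approach". Protocol 7.3.2 says the same.
- **Denominator** (SAP 5.1): "Categorical variables will be summarized by number of participants with observed values, events (n), frequency count (n1), and percentage of participants with observed values".
- **Evaluable month** (SAP 6.4.2.1): "a minimum of 14 days' eDiary data during that period is required for the migraine days to be evaluable". Below that, "the migraine days for that period will be considered as missing".
- **Interval** (SAP 5.3.1): "The 95% CI for percent improvement (decrease) in monthly migraine days at each monthly period will be based on the normal approximation to the binomial". The repeated-measures model in the same section is for continuous endpoints only.

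Diary recording runs until Visit 14, and the device is collected at Visit 14/ET (Protocol 6.5 and 8.4.2.3). A participant who stops early therefore has no later diary months. Protocol 8.8 lists adverse events and "Lack of efficacy" among the reasons for discontinuation.

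**The concern.** Taken together, these rules remove a participant who stops in, say, the fourth month from both parts of the fraction in every later month. If those who leave are disproportionately people who were not responding, the percentage can rise over the year without anyone improving. With no control arm, such a rise cannot be told apart from sustained or growing benefit by looking at the responder table.

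The responder endpoints are also less protected than the key continuous ones. The model for monthly migraine days uses each participant's earlier months and is valid if data are missing at random. The ≥ 50% responder rate gets a point estimate and an interval, but that interval reflects only sampling error among those still observed. At stake is how the Weeks 49-52 responder rate will be read: as a result for everyone who started, or for those who stayed.

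**Working it through.** **Inputs from the documents.** At least 170 enrolled, made up of at least 140 rollover and about 30 de novo participants, "to meet a target of a minimum of 100 participants exposed to atogepant at 1 year" (SAP 3). The documents give no responder rate, dropout rate or split of exit reasons, so there is no figure of the plan's own to reproduce beyond 140 + 30 = 170.

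**Assumptions.** Observed ≥ 50% responder rate of 60% (range 50-70%). Share without evaluable Weeks 49-52 data of 10%, 20% or 41.2%. The last is the largest loss from 170 that still leaves 100: 1 - 100/170 = 41.2%. The mITT population is taken as 170 for illustration.

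**Formula.** Let m be the share missing, p_obs the response rate in those observed and p_mis the rate the missing would have had.

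Full-population rate = (1 - m) × p_obs + m × p_mis

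Gap = p_obs - full-population rate = m × (p_obs - p_mis)

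**Gap in percentage points at p_obs = 60%:**

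| Share missing | p_mis = 0% | 20% | 40% | 60% |
|---|---|---|---|---|
| 10% | 6.0 | 4.0 | 2.0 | 0 |
| 20% | 12.0 | 8.0 | 4.0 | 0 |
| 41.2% | 24.7 | 16.5 | 8.2 | 0 |

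For example, 0.20 × (60 - 20) = 8.0.

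**In whole participants, all missing counted as non-responders:**

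- 10% missing: 92/153 = 60.1% becomes 92/170 = 54.1%.
- 20% missing: 82/136 = 60.3% becomes 82/170 = 48.2%.
- 41.2% missing: 60/100 = 60.0% becomes 60/170 = 35.3%.

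In the last case the SAP's interval for 60/100 would be 50.4% to 69.6%. With observed rates of 50% and 70% the gap there is 20.6 and 28.8 points; at 20% missing it is 10.0 and 14.0.

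**Only lack-of-efficacy leavers counted as non-responders, other missing still excluded.** At 20% missing (34 people), if 3, 8 or 17 of them (about 10%, 25% or 50%) left for that reason:

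- 82/(136 + 3) = 59.0%, a gap of 1.3 points.
- 82/(136 + 8) = 56.9%, a gap of 3.3 points.
- 82/(136 + 17) = 53.6%, a gap of 6.7 points.

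**Trend check.** Suppose 85 of 170 respond early (50.0%), 34 non-responders leave, and nobody's status changes. The observed-case rate becomes 85/136 = 62.5%. This is an extreme case, but it shows that exits alone can move the rate.

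**The case against.** The strongest reply is that this is a choice of estimand and not an error. The efficacy objective concerns treatment administered over 52 weeks, and a rate among people on treatment with diary data answers that question. The SAP is open about it: it names the observed-case approach and defines its percentage as the "percentage of participants with observed values". This is a single-arm safety study with no statistical hypothesis (SAP 2), and its efficacy endpoints are descriptive and unranked (SAP 5.3.1). All of this stands. It is why observed cases should remain the first presentation.

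A reader might go further than the text allows in four ways.

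- **That the rate is inflated as a matter of fact.** The direction depends on leavers responding less often than stayers. That is plausible for those who leave for lack of efficacy, but Protocol 8.8 also lists pregnancy and site or study termination, and Protocol 8.4.4 requires exit after 8 weeks of remote visits for those who cannot attend. The gap is zero if leavers would respond as often as stayers.
- **That nothing in the plan reveals the loss.** The observed n goes with each percentage (SAP 5.1), completion and discontinuation are tabulated with reasons (SAP 5.2), and exposure is reported by duration (SAP 5.4.1). A reader can see the denominator shrink. What is missing is a link from these tables to the responder rate.
- **That the plan expects about 41% attrition.** The 170 and the 100 are both minimums set by exposure requirements, no dropout rate is stated, and Protocol 12.6 attributes the rise from 140 to 170 to adding the de novo cohort.
- **That 60% would become 35%.** That contrast combines the largest loss compatible with the target, failure for every leaver, and enrolment in place of mITT. The mITT population needs an evaluable baseline and one evaluable post-baseline month (SAP 4), so it can be smaller than 170. Some participants without a Weeks 49-52 value may also still be on treatment with fewer than 14 diary days.

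**Conclusion.** The point holds in conditional form. The late-month responder rate is a valid description of participants still on treatment with enough diary data. As an estimate for everyone who started, it is too high by m × (p_obs - p_mis) whenever leavers would respond less often than stayers, and the SAP contains no responder analysis that would show by how much.

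The size cannot be taken from the documents. At the assumed 60% observed rate, 20% missing gives a gap of 0 to 12 points as the missing group's response rate falls from 60% to 0%. About 25 points is the upper bound at that rate, and it needs both 41% loss and no responders among the leavers. Counting only lack-of-efficacy leavers as failures gives about 1 to 7 points at 20% missing. This is worth correcting before the responder rates are reported. It does not affect the study's primary safety objective.

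**What to change.** In SAP 5.3.1 and 5.3.2:

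1. Keep observed cases as the first presentation.
2. Add a supplementary table of the ≥ 50% responder endpoint at each month, by cohort, with all mITT participants as the denominator. The other cut-offs are optional.
3. Count participants who have discontinued treatment as non-responders from that point.
4. State the rule for participants still on treatment whose month is not evaluable, for example counted as non-responders and shown as a separate count.
5. Wherever the Weeks 49-52 rate is reported, give both figures with the evaluable n.

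The cost is one extra table per cohort from data already collected. The added figure is conservative, because exits unrelated to effect count as non-response, so it belongs beside the observed-case rate and not in its place. It also does not reach treated participants who never had an evaluable month, since they are outside mITT. The Safety and mITT counts already planned in SAP 5.2 will show how many there are.
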